Prior to commencing any exercise all participants will undergo a physical examination and will be required to complete an on medication screening graded exercise test per previously established protocols (Schenkman, M., et al., 2008; Christiansen, C.L., et al., 2009; Katzel, L.I., et al., 2001) in order to determine whether or not they can exercise.

A single 90 minute fMRI session will be completed first. During this session, participants will have 2 structural scans: a T1-weighted (T1W) sagittal, magnetization prepared rapid acquisition with gradient echo (MP-RAGE, TR=2400 ms, TI=1000 ms, TE=3.16 ms, FA=15°, 1.0 mm³ voxels, 8:09 min) and a T2-weighted (T2W) fast spin echo (TR=3200 ms, TE=455 ms, 1.0 mm³ voxels, 4:43 min). Two functional connectivity scans will be acquired via BOLD sensitized fMRI (TR=2200 s, TR=25 ms, 4.0 mm³ voxels, 7-min runs of 194 frames). During these scans, participants will remain still and keep their eyes closed. Participants will be visual monitored via an eye tracking device during data acquisitions and will be given an emergency indicator which can be pressed at any time to stop the scans. During the imagined walking component 9 minutes of eco-planar imaging data will be acquired (TR=2200ms, TE=2.5ms, 4 mm³ voxels) will be acquired while the participant views the cue or null condition on a mirror mounted to the head coil.

All individuals will then complete the following battery of questionnaires and assessments(approximately 90 minutes):

Montreal Cognitive Assessment
Wechsler Test of Adult Reading (WTAR)
Spatial Delayed Response Task (SDR)
Nback Working Memory Test (Nback)
Trail Making Test
Stroop Test
Go-No-Go (GNG)
Verbal Fluency
RMswitch task
Frontal Systems Behavior Scale (FrSBe)

All individuals will complete the clinical assessments listed below as well as gait and balance testing consisting of the following (approximately 1 hour):

RMswitch task
Go-No-Go (GNG)
Spatial Delayed Response Task (SDR)
Nback Working Memory Test (Nback)
Mini Mental Status Exam (MMSE)
The New Freezing of Gait Questionnaire (nFOG_Q)

Mini BESTest

The Smell Threshold Kit

Movement Disorder Society Unified Parkinson Disease Rating Scale (MDS-UPDRS)

Five times sit to stand (5xSTS) - 6 minute walk (6MWT) - 9 Hole Peg Test (9HPT)

PDQ-39

Forward preferred speed, forward fast, backward, tandem and dual task walking on a GAITRite computerized walkway system.

Spatiotemporal gait assessment will be completed simultaneously with the GaitRITE assessment.

F5 Intervention

Each Participant will be assigned to a group (treadmill training, tango dance training or stretching) using a process of stratified blocked randomization and notified of their group assignment following their initial visit. This is necessary as walking speed must first be assessed prior to group assignment.

Within one week of the initial visit, the training sessions will begin. All groups will receive 12 weeks of exercise, meeting 3 times per week for one hour each session. The exercise groups will thus participate in 180 minutes of exercise per week, meeting the CDC guidelines for physical activity. All groups will exercise in community-based group settings to ensure that participants have similar experiences with respect to social interactions associated with participating in a group exercise class

The individual groups will complete 1 hour of training following the protocol listed below:

Tango Training: Tango classes will be modeled on those of our previous studies, and will include a brief warm up and a cool down, with 45 minutes of the hour devoted to tango specifically as described previously in our lab. Participants will dance both leading and following roles and will change partners frequently in order to ensure that everyone spends time moving forward and backward and gets experience dancing with many different partners. Partners will be individuals without PD and will include spouses and caregivers of those with PD as well as healthy volunteers.

Treadmill Training: The treadmill training group will have the same warm up and cool down period as the tango group with 45 minutes of the hour devoted to walking on the treadmill. Participants will walk on the treadmill at their own self-selected comfortable pace. Overground walking speed will be reassessed every 2 weeks and treadmill speed adjusted as needed to ensure that it continues to match overground walking speed. This model of treadmill training was chosen for two reasons: 1) to be of comparable intensity to the tango class where the basic dance step is walking done at preferred pace and 2) because recent evidence suggests that training at preferred speed for longer durations is more effective in enhancing gait than training at higher intensity for shorter blocks of time. The periodic reassessment of overground preferred speed and subsequent adjustment of treadmill speed will help to ensure that the treadmill training is also progressive in nature and in that way mirrors the progressive nature of the tango classes as much as possible.

Stretching Group: The stretching class will also have the same warm up and cool down as the other groups, with 45 minutes devoted to stretching and flexibility exercises taken from the Be Active and Fitness Counts programs.

F6 Visit 2 – Post-Intervention Evaluation

A single 90 minute fMRI session will be completed first. During this session, participants will have 2 structural scans: a T1-weighted (T1W) sagittal, magnetization prepared rapid acquisition with gradient echo (MP-RAGE, TR=2400 ms, TI=1000 ms, TE=3.16 ms, FA=15°, 1.0 mm³ voxels, 8:09 min) and a T2-weighted (T2W) fast spin echo (TR=3200 ms, TE=455 ms, 1.0 mm³ voxels, 4:43 min). Two functional connectivity scans will be acquired via BOLD sensitized fMRI (TR=2200 s, TR=25 ms, 4.0 mm³ voxels, 7-min runs of 194 frames). During these scans, participants will remain still and keep their eyes closed. Participants will be visual monitored via an eye tracking device during data acquisitions and will be given an emergency indicator which can be pressed at any time to stop the scans. During the imagined walking component 9 minutes of eco-planar imaging data will be acquired (TR=2200ms, TE=2.5ms, 4 mm³ voxels) will be acquired while the participant views the cue or null condition on a mirror mounted to the head coil.

All individuals will then complete the following battery of questionnaires and assessments(approximately 90 minutes):

Montreal Cognitive Assessment
Wechsler Test of Adult Reading (WTAR)
Spatial Delayed Response Task (SDR)
Nback Working Memory Test (Nback)
Trail Making Test
Stroop Test
Go-No-Go (GNG)
Verbal Fluency
RMswitch task
Frontal Systems Behavior Scale (FrSBe)

All individuals will complete the clinical assessments listed below as well as gait and balance testing consisting of the following (approximately 1 hour):

RMswitch task
Go-No-Go (GNG)
Spatial Delayed Response Task (SDR)
Nback Working Memory Test (Nback)
Mini Mental Status Exam (MMSE)
The New Freezing of Gait Questionnaire (nFOG_Q)
Mini BESTest
The Smell Threshold Kit
Movement Disorder Society Unified Parkinson Disease Rating Scale (MDS-UPDRS)
Five times sit to stand (5xSTS) - 6 minute walk (6MWT) - 9 Hole Peg Test (9HPT)
PDQ-39
Forward preferred speed, forward fast, backward, tandem and dual task walking on a GAITRite computerized walkway system.
Spatiotemporal gait assessment will be completed simultaneously with the GaitRITE assessment.

F7 Visit 3 – Follow-up

A follow-up visit will be scheduled for 12 weeks after the final exercise class has been completed.

All individuals will complete the following battery of questionnaires and assessments (approximately 90 minutes):

Montreal Cognitive Assessment
Wechsler Test of Adult Reading (WTAR)
Spatial Delayed Response Task (SDR)
Nback Working Memory Test (Nback)
Trail Making Test
Stroop Test
Go-No-Go (GNG)
Verbal Fluency
RMswitch task
Frontal Systems Behavior Scale (FrSBe)

All individuals will complete the clinical assessments listed below as well as gait and balance testing consisting of the following (approximately 1 hour):

RMswitch task
Go-No-Go (GNG)
Spatial Delayed Response Task (SDR)
Nback Working Memory Test (Nback)
Mini Mental Status Exam (MMSE)
The New Freezing of Gait Questionnaire (nFOG_Q)
Mini BESTest
The Smell Threshold Kit
Movement Disorder Society Unified Parkinson Disease Rating Scale (MDS-UPDRS)
Five times sit to stand (5xSTS) - 6 minute walk (6MWT) - 9 Hole Peg Test (9HPT)
PDQ-39
Forward preferred speed, forward fast, backward, tandem and dual task walking on a GAITRite computerized walkway system.
Spatiotemporal gait assessment will be completed simultaneously with the GaitRITE assessment.

F8 Safety and Adverse Events

8.a Safety and Compliance Monitoring

8.b Medical Monitoring

Effects of medication withdrawal will be monitored via patient report and if the effects are too severe, participation in the study will be terminated prior to the second day of "off medication" testing.

8.c Definitions of Adverse Events

An adverse event is any patient reported

8.d Classification of Events

We do not anticipate any adverse events; however, the following procedures will be followed to minimize the risk.

- a) Temporary Worsening of Parkinson's symptoms. A temporary worsening of Parkinson's disease symptoms may result from not taking anti-Parkinson's medication for study evaluations. Once the individual resumes taking their medication, symptoms should return to their typical levels. Effects of medication withdrawal will be monitored and if the effects are too severe, participation in the study will be terminated prior to the second day of "off medication" testing .
- b) Loss of confidentiality. Loss of confidentiality is highly unlikely. To safeguard against this, we will comply with all HIPAA regulations. Data will not be identified by subject name. All data will be coded, and code sheets will be stored in locked files.
- c) Stumbling during locomotion. Subjects will be closely attended by a physical therapist during walking. Walking will be performed in a large, open space and the therapist will be prepared to assist subjects who may stumble. It is therefore unlikely that subjects will experience falls during testing or will be injured as the result of a fall.
- d) Falling into safety harness. During testing on the treadmill, subjects will wear a modified parachute harness connected to an overhead beam that is rated to support heavy loads. A subject who falls will be supported fully by the harness and is therefore unlikely to be injured. Subjects will also be able to hold the support guides which will help them to stabilize balance during treadmill testing. In addition, the treadmill will be equipped with redundant safety features to prevent subject injury and allow immediate cessation of treadmill movement at the touch of a button.
- e) Mechanical injury involving moving apparatus. The treadmill is equipped with a safety switch that, when pressed, will immediately stop treadmill movement. The treadmill is also equipped with a break that can be applied at any time. Treadmill design is such that accelerations and decelerations are not abrupt, but are smooth, non-jarring transitions. Furthermore, it will be laboratory policy that: 1) the PI or another lab member will always be the first test subject for any new protocol and 2) on the day of an experiment, the exact protocols to be used will first be run without a subject to ensure proper system function.
- f) Skin irritation may be prevented by notifying investigators of any potential allergens due to adhesive or alcohol (i.e. skin preparation).
- g) Fatigue. The proposed study involves one-hour exercise training sessions. Rest breaks will be provided as frequently as needed but you still are likely to be tired

afterwards. Some of the proposed studies involve stretching, stepping or walking for periods of time up to 60 minutes and this may result in fatigue for some subjects. Rest breaks will be provided as frequently as possible and no subjects with history or indication of orthostatic hypotension will be admitted to the studies. Fatigue during the MRI may also occur. We will maintain contact with the participant through out the session to monitor them. Additionally we can remove the individual from the scanner if they report being too sleepy to continue.

h) Dizziness. At the completion of the test, when the subject may be a little dizzy, investigators will walk very near the subject to the outer room and make sure the subject is not dizzy before he/she is dismissed.

i) Claustrophobia. All individuals will be screened for previous claustrophobic experiences prior to participation. During the scanning sequence all participants will have an emergency squeeze bulb in their hand that, when squeezed, will notify the researchers of their distress. We will immediately remove the individual from the scanner at this time.

j) Loud noise. While inside the magnet, subjects will be able to communicate with the investigators through an intercom. To help protect the participant's hearing two levels of hearing protection will be worn by all participants. Ear plugs will be inserted into the ear and outer headphones will be placed over your ears. Also, they will be given an alarm device to press if the intercom system should be ineffective because of the loud noises. This alarm will create a definite signal to the investigators that the subject wishes to communicate or exit. If a test is in progress, the test will be stopped and investigators will either speak to the subject using the intercom or enter the room and take the patient out of the magnet.

The risks associated with these studies are minimal. Participant safety will be continuously monitored by the PI during experimental sessions and participants will be advised of how to contact the PI if they have any concerns that arise outside of these sessions.

8.e Reporting Procedures

Any adverse events will be reported to the local IRB immediately and will trigger an immediate review, like the annual review described previously, to determine what changes need to be made and whether the study should continue or conclude.

8.f Adverse Event Reporting Period

Patients will be followed for 12 weeks following their final exercise session. Adverse events will be documented throughout this period.

8.g Post-study Adverse Event

Any advent reported to the investigators following the conclusion of the study will be documented and reviewed.

G Statistical Plan

G1 Sample Size Determination and Power

Using PASS software (NCSS, LLC, Kaysville, UT), we have powered each aim based upon preliminary data. Our primary variable of interest in Aim 1 is gait velocity. Average forward gait velocity +/- SD was 1.2 +/- 0.1 m/s and average backward gait velocity was 0.6 +/- 0.1 in a sample of 60 individuals with PD (H&Y = 2.4 +/- 0.2) tested OFF medication in our laboratory over the past year for a different study. The study has been powered to be able to detect differences of 1 SD, or 0.1 m/s, which is equivalent to an effect size of 0.4. Changes of 0.1m/s or more in gait velocity have been reported previously following both tango [22-24] and treadmill training [8, 29, 61, 62]. With an effect size of 0.4, 27 participants per group will provide 89% power to detect differences between or within groups using two-tailed tests at a significance level of 0.05. Based upon additional preliminary data from our lab, we have determined that this sample size is also more than sufficient to adequately power our secondary variables in Aim 1 (MDS-UPDRS-III, mini-BESTest, PDQ-39).

Aims 2 and 3 have been powered based upon preliminary data from our lab and sources in the literature. For Aim 2, our preliminary data from controls before and after a single session of treadmill training indicate an effect size of 0.91 for change in beta weights using the cerebellum as an exemplar region (pre = -0.094 +/- 0.111, post = 0.418 +/- 0.116, Figure 9) during imagined forward walking. We recognize that responses in those with PD may be less pronounced than in controls and as such have used a very conservative effect size of 0.45, half the size of the effect observed in controls, for our power calculation. Our preliminary data from people with PD (n=8) imagining forward walking indicate a beta weight of -0.075 +/- 0.097, which is comparable to the value obtained from young controls at baseline. Utilizing the data from the sample with PD and an estimated effect size of 0.45, 18 subjects per group will provide 80% power to detect differences between groups and 88% power to detect within group differences.

Significant findings of differential BOLD signal changes have been localized in PD populations during similar imagined walking MRI paradigms with a total of 12 PD participants per group [59], further supporting that our proposed sample size is likely adequate. For Aim 3, utilizing rs-fcMRI (Figures 7,8) to determine correlations between regions in the locomotor control network, we have powered the study to enable detection of differences in correlation coefficients of 0.1 (mean correlation = 1.0, SD = 0.1, p = 0.05, effect size = 0.44, per data from Wu et al. 2009 and our own preliminary data). We will have 80% power to detect between group differences and 88% power to detect within group differences with 18 subjects per group.

Based upon our previous intervention studies [23], we anticipate an attrition rate of approximately 15-20% due to dropouts or failure to complete the required minimum of 85% of classes. We also expect MRI related complications due to head motion in roughly 30% of tested individuals. This estimate is based upon our preliminary data from individuals with PD (Fig. 4, 5) where we lost 24% of scans due to head motion greater than 2mm of translation or rotation during a scan. As such, we will recruit 40 subjects per group to account for attrition and data loss due to head motion and still obtain the needed final sample sizes for each aim. For Aim 1 dropouts will be handled utilizing intent to treat analyses with the last observation carried forward. Dropouts will be excluded from analyses in Aims 2 and 3 as full imaging data are needed from two time points.

G2 Interim Monitoring and Early Stopping

The protocol will also be evaluated and the risk to benefit ratio assessed twice annually.

G3 Analysis Plan and Statistical Methods

For **Aim 1**, we will employ a repeated measures ANOVA with group (tango, treadmill, and *stretching*) and time (pre-intervention, post-intervention, and *follow-up*) as factors to determine whether and how these interventions impact gait velocity, our primary variable for Aim 1. Similar analyses will also be performed for secondary variables of interest, including the MDS-UPDRS-III, mini-BESTest, and PDQ-39. *As a secondary analysis for gait velocity, MDS-UPDRS-III, and mini-BESTest, we will determine percent difference between OFF and ON medication values at pre-intervention and post-intervention time points and compare these difference values using RM ANOVAs with group and time as factors. (If prescribed medications change over the course of the study then levodopa equivalent daily dose will be included as a covariate in these analyses.) This will allow us to determine if response to medications was different before vs. after intervention and whether this effect differed between groups.* Analyses will be conducted using NCSS software (NCSS, LLC, Kaysville, UT). All imaging analyses will be conducted using Brain Voyager (Brain Innovation, Maastricht, The Netherlands) and custom written Matlab (MathWorks, Natick, MA) software. For **Aim 2**, we will apply random effects general linear model analysis using forward and backward imagined tasks as individual contrasts. A false discovery rate (FDR) correction will be used to compensate for multiple comparisons. BOLD signal changes within the previously specified regions of interest will be compared for pre- and post-intervention conditions. Additionally, the three groups will be compared to each other in the post-intervention condition using RFX ANCOVA. For **Aim 3**, we will use an independent component analysis (ICA) to examine the strength of the correlation coefficients for anatomical regions identified as part of the locomotor control network. The strength of these correlations before vs. after intervention will be compared via two-tailed RM ANOVAs with group and time as factors. Finally, we will correlate BOLD signal changes during the imagined walking tasks (Aim 2) and changes in connectivity (Aim 3) with changes in motor performance.

G4 Missing Outcome Data

For Aim 1 dropouts will be handled utilizing intent to treat analyses with the last observation carried forward. Dropouts will be excluded from analyses in Aims 2 and 3 as full imaging data are needed from two time points.

H Data Handling and Record Keeping

H1 Confidentiality and Security

All data and data monitoring will be kept strictly confidential according to HIPAA regulations. Results will be coded and the code sheets will be stored in locked files.

H2 Training

All investigators involved with this study will complete safety training, HIPAA requirements and will undergo yearly training by the PI in data handling and safeguarding.

H3 Case Report Forms and Source Documents

Any adverse events will be reported to the local IRB immediately and will trigger an immediate review to determine what changes need to be made and whether the study should

H4 continue or conclude. Records Retention

Data will not be identified by participant name. All data will be coded, and code sheets will be stored in locked files behind a locked door. Records will be stored for a minimum of seven years.

H5 Performance Monitoring

Participant safety will be continuously monitored by the PI and participants will be advised of how to contact [name] if they have any concerns that arise outside of these sessions. Data quality will also be assessed on an ongoing basis, as data will be processed immediately after each experimental session. In addition, [name] and [name] will conduct a twice yearly review of data to ensure that the studies are progressing in a timely manner. The protocol will also be evaluated and the risk to benefit ratio assessed twice annually. All data and data monitoring will be kept strictly confidential according to HIPAA regulations. Results will be coded and the code sheets will be stored in locked files.

I Study Monitoring, Auditing, and Inspecting

I1 Study Monitoring Plan & Auditing and Inspecting

The risks associated with these studies are minimal, as detailed in the Human Subjects Research section of the application. Participant safety will be continuously monitored by the PI and participants will be advised of how to contact [name] if they have any concerns that arise outside of these sessions. Data quality will also be assessed on an ongoing basis, as data will be processed immediately after each experimental session. In addition, [name] and [name] will conduct a twice yearly review of data to ensure that the studies are progressing in a timely manner. The protocol will also be evaluated and the risk to benefit ratio assessed twice annually. Any adverse events will be reported to the local IRB immediately and will trigger an immediate review to determine what changes need to be made and whether the study should continue or conclude. All data and data monitoring will be kept strictly confidential according to HIPAA regulations. Results will be coded and the code sheets will be stored in locked files.

J Study Administration

J1 Funding Source and Conflicts of Interest

DHHS, National Institutes of Health

J2 Subject Stipends or Payments

All participants will be paid \$75 for each completed MRI session and \$50 for the follow-up evaluation. The maximum possible compensation amount equals \$200.

Individuals able to begin an MRI session but who withdraw during the session will be compensated \$25 for their time.

J3 Study Timetable

Table 2. Project Timeline	Year 1	Year2	Year3	Year4	Year5
Standardize Protocol train Personnel	X				
Recruit Participants	X	X			
Evaluate Participants	X	X	X	X	
Deliver Exercise Interventions		X	X	X	
Data Entry/Verification	X	X	X	X	
Analyze Data				X	X
Prepare & Submit Manuscripts					X

K Publication Plan

Preparation and submission of manuscripts is projected to occur in the fifth year of the study.

L Attachments (attached to HRPO document)

L1 Informed consent documents

One consent document version for all participants.

L2 Questionnaires or surveys

Epworth Sleepiness Scale
Non-Motor Symptom Questionnaire
Stages of Readiness to Exercise Questionnaire
Fall History Questionnaire

The New Freezing of Gait Questionnaire (nFOG_Q)
Mini Mental Status Exam (MMSE)
Five times sit to stand (5xSTS) - 6 minute walk (6MWT) - 9 Hole Peg Test (9HPT)
PDQ-39
Footedness/Handedness Questionnaire
Movement Disorder Society Unified Parkinson Disease Rating Scale (MDS-UPDRS)

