Parkinson disease (PD) is a progressive, neurodegenerative disorder that affects 1-1.5 million people in the United States. Difficulty with walking has been recognized as one of the earliest signs marking onset of disability in people with PD [1]. Walking difficulties and other symptoms are not fully addressed by current treatment approaches [2, 3], making clear the need for additional approaches. Exercise is one such approach. Current literature supports use of exercise as an adjunct to traditional treatments for improving gait, balance, and quality of life [4]. The primary aims of the proposed work are to compare the effects of three community based exercise programs on locomotor function and to determine whether and how these interventions alter the function and connectivity of locomotor control networks in the brain. To this end, we will utilize task-based functional magnetic resonance imaging (fMRI) and resting state functional connectivity (rs-fc) MRI to assess brain function and connectivity before and after the exercise interventions.

One hundred twenty people with PD will be randomly assigned one of three community-based exercise groups: tango dancing, treadmill training or stretching (control). Tango has been chosen because evidence suggests tango may be superior to a more traditional exercise program for improving gait, balance and quality of life [5, 6]. Treadmill training has been chosen because studies suggest that it can improve gait and quality of life [7]. Stretching has been chosen for the control group because it is an intervention that does not directly target walking and will allow us to control for the social and attentional aspects of participating in group exercise. Each group will receive 3 months of intervention, attending tri-weekly one-hour group classes. Each participant will be evaluated at three time points over 6 months. MRI and behavioral measures will be conducted with participants OFF medication, with behavioral measures also assessed ON medication.

A2 Primary Hypothesis

Hypothesis 1a: Both tango and treadmill training will improve forward walking performance, but only tango will improve backward walking performance. Walking performance in the stretching group will not change.

Hypothesis 1b: Tango and treadmill training will similarly improve disease severity. Tango will result in larger improvements in balance and quality of life compared to treadmill training and stretching.

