populations with neurological disorders [11, 12]. In healthy controls, la Fougère et al. [9] compared real walking using positron emission tomography to imagined walking during functional magnetic resonance imaging and concluded that while some differences were apparent in the final motor pathways, the two tasks resulted in activation of very similar locomotor networks. The advent of resting state functional connectivity, which assesses activity at rest and therefore eliminates the need to evoke real or imagined locomotor behaviors, presents another viable means of assessing locomotor networks using imaging. Rs-fcMRI, as its name implies, measures activity at rest and only requires that participants lie quietly in the scanner. Rs-fcMRI focuses on spontaneous fluctuations in the blood oxygen level dependent (BOLD) signal at rest. These spontaneous fluctuations are not random, but rather are correlated among functionally related regions. Previous rs-fcMRI results have shown correlations equal to those seen during task-based MRI [13, 14]. These spontaneous fluctuations show coherence across areas of the brain known to be not only functionally related, but also anatomically connected as demonstrated by studies combining rs-fcMRI with diffusion tensor imaging (a technique used to trace white matter tracts) [14]. Rs-fcMRI identifies related networks within the resting state BOLD data, providing insight regarding the neuronal activation patterns of different brain regions and reflecting the amount of functional communication between these regions [15]. Rs-fcMRI techniques have been used to successfully identify several networks, including the visual, auditory, default mode, and motor networks, among others [15, 16]. Rs-fcMRI methods have also been employed in groundbreaking studies examining connectivity in disease states such as Alzheimer disease, schizophrenia, depression, and several others yielding key advances in our understanding of these conditions (for review see [16]). Rs-fcMRI holds great promise as a potential biomarker for progression of disease, elucidating compensatory mechanisms associated with disease processes, informing targeting of neurosurgical treatments, and investigating new treatment strategies. Although used successfully in many other populations with neurological disorders, rs-fcMRI has been little utilized to date to study PD. We are excited about the possibility of utilizing rs-fcMRI to study individuals with PD. We will combine measures of imagined walking (Aim 2) with measures of resting state functional connectivity (Aim 3) to gain a fundamental understanding of the human locomotor control network in PD and how it is altered by exercise. Both the imagined and the resting state tasks have the benefit of not requiring any actual motor output from the participants, thus limiting the extent to which the effects of the disease on movement production might confound the data collection process.

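### The plan expects head-motion problems in about 30% of those scanned but states no motion term for its imaging models or brain-behaviour correlations, so residual motion could produce spurious correlations under Hypotheses 2b and 3b

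*Combined protocol and SAP*

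**What the plan says.** - **Choice of task (B1).** Imagined walking and rest are preferred because the participant does not have to move, "thus limiting the extent to which the effects of the disease on movement production might confound the data collection process".
- **Scanning conditions (E1, F4, F6).** MRI is done OFF medication, before and after the intervention. Participants are asked to keep still during the resting scans.
- **Head motion (G1).** In the PD pilot, "we lost 24% of scans due to head motion greater than 2mm of translation or rotation during a scan". For the trial, "We also expect MRI related complications due to head motion in roughly 30% of tested individuals". The response is on sample size: "we will recruit 40 subjects per group to account for attrition and data loss due to head motion". The 2 mm figure describes pilot losses; neither G3 nor G4 makes it a rule for the trial.
- **Imaging analyses (G3).** Aim 2 uses a random-effects general linear model with FDR correction and a post-intervention RFX ANCOVA whose covariates are not named. Aim 3 uses ICA, and then "The strength of these correlations before vs. after intervention will be compared via two-tailed RM ANOVAs with group and time as factors". Imaging changes are finally correlated with changes in motor performance. No motion regressor, motion covariate or comparison of motion between arms is stated.
- **Hypotheses (A2).** Hypothesis 1b says "Tango and treadmill training will similarly improve disease severity". Hypotheses 2a and 3a predict imaging change in those two arms, in different regions, and none with stretching. Hypotheses 2b and 3b predict that imaging change is related to change in locomotor performance.

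**The concern.** Recruiting extra people replaces lost scans; it does nothing about motion in the scans that are kept. A scan with motion just under 2 mm enters the analysis on the same footing as a still one.

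Randomisation balances motion between arms at baseline, in expectation. The risk arises afterwards. The plan expects severity to improve in the two active arms. If people with milder signs also move less in the scanner, motion will change in those arms and not with stretching.

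Hypotheses 2b and 3b are more exposed. They relate change to change across individuals, a comparison that randomisation does not protect. A participant whose PD improves may both walk faster and lie stiller. If motion affects BOLD or connectivity estimates, imaging change and gait change will correlate even when the locomotor network has not altered. A positive result could not then be told apart from a shared change in motion.

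**Working it through.** **1. The plan's own figures.** G1 gives Aim 3 an effect size of 0.44, 18 per group, 0.05 two-sided and 80% between-group power. Reading the effect size as Cohen's f in a three-group F test, λ = f² × N = 0.44² × 54 = 10.45 on 2 and 51 df. Power is 80.9%, so the figure reproduces. For Aim 2, where "an estimated effect size of 0.45, 18 subjects per group will provide 80% power to detect differences between groups", the same formula gives 82.8%, slightly above the stated value.

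**2. Does the recruitment allowance cover lost scans?** G1 says "we anticipate an attrition rate of approximately 15-20% due to dropouts or failure to complete the required minimum of 85% of classes". Usable n per arm = 40 × (1 − attrition) × (1 − motion loss):
- 15% attrition, 30% of individuals: 40 × 0.85 × 0.70 = 23.8
- 20% attrition, 30% of individuals: 40 × 0.80 × 0.70 = 22.4

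Both exceed 18. If the pilot's 24% applies to each scan, both scans are needed and losses are independent, the loss is 1 − 0.76² = 42.2%, leaving 19.6 to 18.5. On G1's own reading of 30% of individuals, the allowance covers the number of scans. What remains open is motion inside retained scans.

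**3. Brain-behaviour correlations.** The documents give no correlation between motion and either measure, so these are assumptions. Let motion change correlate a with imaging change and a with gait change, with no other link between the two. Then the spurious r = a × a. Pool the arms, N = 3 × 18 = 54 (also an assumption; G3 does not say whether arms are pooled). Fisher's z gives z = atanh(r) × √51, tested at 1.96.

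| a | spurious r | z | significant |
|---|---|---|---|
| 0.3 | 0.09 | 0.64 | 9.9% |
| 0.4 | 0.16 | 1.15 | 21.1% |
| 0.5 | 0.25 | 1.82 | 44.6% |

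The partial correlation has numerator r − a² = 0, so controlling for motion change removes the artefact. Simulation with 6,000 runs per setting agrees: about 10%, 21% and 46% significant for the simple correlation, and about 4% to 5% for the partial correlation.

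**4. Group comparisons.** Assume motion correlates 0.3 to 0.5 with a connectivity value and falls by 0.3 to 0.5 SD in both active arms only. The spurious shift d is the product of the two: 0.3 × 0.3 = 0.09, 0.3 × 0.5 = 0.15, 0.5 × 0.5 = 0.25 SD. With arm pattern (d, d, 0) and 18 per arm, λ = 18 × (2/3) × d² = 12d².

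| d | λ | three-arm F test rejects |
|---|---|---|
| 0.09 | 0.097 | 5.7% |
| 0.15 | 0.270 | 7.0% |
| 0.25 | 0.750 | 10.7% |

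The tango-versus-treadmill bias under this pattern is d − d = 0.

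**5. Power cost of one motion covariate.** Error df falls from 51 to 50. Aim 3 power goes from 80.93% to 80.88%, and Aim 2 from 82.75% to 82.70%, before any gain from explained variance.

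**The case against.** The strongest reply has four parts.

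- **The hypothesised pattern is regional.** Hypotheses 2a and 3a predict premotor, supplementary motor and putamen change after tango, and somatosensory and cerebellar change after treadmill training. A reader might infer that a motion shift in both active arms would mimic the hypothesised result. It would not: a shared shift does not produce that dissociation and leaves tango versus treadmill unbiased. This stands, and it limits the between-arm concern to comparisons with stretching.
- **The mechanism is assumed.** No section links head motion to severity or gait, or shows that less motion would raise BOLD or connectivity. The pilot loss is reported without a healthy comparator. This also stands. The figures above show what could happen, not what will.
- **Silence is not absence.** The ANCOVA covariates are unnamed and preprocessing is not described; a stereotaxic atlas is in the reference list without a citation in the available text. Motion correction may be documented elsewhere. So the supportable statement is that no motion term is stated, not that none will be used.
- **Adjustment has its own risk.** If training changes motion, motion is a post-randomisation variable. Adjusting for it may remove real effect or add bias in either direction. This stands against making the adjusted analysis the only or primary group comparison. It does not stand against showing it beside the planned one.

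The 30% allowance and the instruction to lie still also count for the plan. They address gross motion, but not what remains in retained scans.

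**Conclusion.** The gap is real and inexpensive to close. By its own figures the plan expects substantial head motion, and it states no way of separating residual motion from imaging change. The main exposure is Hypotheses 2b and 3b, with roughly 10% to 45% false-positive correlations in place of 5%. The three-arm comparison is less exposed, at about 6% to 11%. All of these rest on assumed motion correlations of 0.3 to 0.5 and, for the group test, an assumed fall of 0.3 to 0.5 SD in both active arms; the true size is unknown. Imaging belongs to the secondary aims (C2), so the primary gait-velocity analysis is untouched.

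A reader might also infer that the pilot's 24% loss contradicts section B1. It does not. B1 speaks of movement required by the task and claims only to limit confounding; involuntary head motion is a different problem. That sentence needs no correction.

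**What to change.** In G3:

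1. Write the 2 mm limit as an analysis rule for the trial, stating whether it applies per run or per session.
2. State which motion correction is applied in preprocessing and which covariates enter the Aim 2 ANCOVA.
3. For Hypotheses 2b and 3b, report partial correlations controlling for change in mean frame-to-frame displacement, beside the simple correlations.
4. For the Aim 2 and Aim 3 group comparisons, keep the unadjusted result and add a prespecified sensitivity analysis with mean displacement as a covariate. A scan-level covariate does not fit a classical group-by-time ANOVA, so for Aim 3 use change in displacement in a change-score model, or a time-varying covariate in a mixed model.
5. Report displacement and motion exclusions by arm and visit.

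The cost is SAP text, one variable derived from existing scan data, and one error degree of freedom in each adjusted model (under 0.1 percentage point of power). The downside is that adjustment may remove some true effect or add bias if training itself alters motion, which is why both versions are reported.
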